The impact of head injury on respiratory mechanics has been studied in just a few clinical investigations. (1-3) Of note, the earliest of these noted that the ventilation perfusion (V/Q) matching following TBI was not the result of lung collapse or parenchymal lung disease but secondary to alterations in perfusion. There are three possibilities for this finding:

1. redistribution in regional perfusion, which is partially mediated by the hypothalamus
2. pulmonary microembolism, leading to increased dead space
3. lung surfactant depletion due to excessive sympathetic stimulation and hyperventilation.

The introduction of inhaled pulmonary vasodilators such as inhaled nitric oxide or aerosolized epoprostenol offer an opportunity to improve oxygenation in patients with TBI without increasing airway pressures in the face of V/Q inequalities.

In 1983, Cooper and Boswell demonstrated that hypoxemia in a series of 21 patients with head injury was related to a decrease in functional residual capacity and increased shunt. (2) In this study the addition of 10 cm H₂O PEEP reversed the fall in FRC and improved oxygenation. However, these patients were all paralyzed and nursed in the supine position. Paralysis and the supine position are known to decrease FRC even in normal subjects under anesthesia.

More recently, Koutsoukou et al evaluated 21 subjects with brain injury (intracranial hemorrhage and TBI) and no evidence of acute lung injury and found that PEEP of 10 cm H₂O prevented a deterioration in respiratory mechanics at five days. On day 1, PaO₂/FIO₂ was > 400 (FIO₂= 0.46) but both lung elastance and airways resistance were slightly elevated in both groups. These findings are not

unexpected in the presence of an endotracheal tube in a sedated subject lying in bed head up. These changes in respiratory mechanics worsened after day 5 and only elastance was spared in the group receiving 10 of PEEP. (3)

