Research personnel will remain at the bedside throughout the measurements of respiratory mechanics which will require approximately 30 minutes to complete.

11. Data Safety monitoring plan and/or DSMB:

[name] will act as medical monitor for the study. He will review subjects' research data and adverse events to ensure patient safety. The medical

monitor will have the power to temporarily or permanently halt enrollment if it is deemed that patient safety is compromised.

12. Data Analysis:

Descriptive statistics will be employed to summarize relevant patient demographic factors as well as on baseline measurement of clinical variables. As a check on the success of randomization, these variables will be compared between groups using t-tests or chi-square tests, as appropriate.

The primary endpoint for this study is a change in $\text{PaO}_2:\text{FiO}_2$ ratio of 20 percent or greater between baseline and Day 3. The proportions of patients achieving success according to this criterion will be compared between groups using a two-sided z-test with pooled variance.

Group sample sizes of 19 in group one and 19 in group two achieve 82% power to detect a difference between the group proportions of 0.40. The proportion in group one (the treatment group) is assumed to be 0.10 under the null hypothesis and 0.50 under the alternative hypothesis. The proportion in group two (the control group) is 0.10. The test statistic used is the two-sided Z test with pooled variance. The significance level of the test was targeted at 0.05. The significance level actually achieved by this design is 0.0361.

Respiratory mechanics will be presented as descriptive (Mean, SD, range). Up to 43 subjects may be enrolled, in order to obtain the required 38 evaluable subjects. Patients will be removed from the study and its analysis if extubated by the clinical treatment team during the 72 hour NO protocol.

13. Data storage and confidentiality (include sample storage if applicable)

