We will ensure that paper forms are stored securely under lock and key when not in the direct custody of an investigator. Forms may have direct identifiers for the purposes of linking data from different medical records. Electronic data will not be entered with direct identifiers. A subject number will be used to link back to the identifier. The key linking identifier to subject number will not be stored with the electronic data. Electronic data will be stored in a password protected Redcap database. Analytical datasets will be stored on secure servers that also limit access to the investigator team. Should results of the study be published or reported, individual names or other identifying information will not be used. One year after the study and publication are complete the data will be destroyed.

14. Study Population

All subjects ≥ 18 and ≤ 75 years of age, admitted to the University of Cincinnati Medical Center with traumatic head injury requiring mechanical ventilation within 24 hours of admission will be screened for enrollment. Inclusion criteria will include:

1. TBI with head CT findings of injury by penetrating or blunt mechanism
2. Requiring mechanical ventilation within 24 hours of admission
3. Negative pregnancy test

Exclusion criteria will include:

1. Brain death
2. Expected survival < 48 hours
3. Pneumothorax causing chest tube to be placed
4. Elevated inspired oxygen concentration ($\text{FiO}_2 > 0.65$) on assessment
5. Hemodynamic instability (systolic BP < 100 mmHg, cardiac arrhythmias)
6. Uncontrolled ICP (>20 mmHg) necessitating bolus hypertonic saline therapy
7. Unilateral or bilateral pupil dilation and no reactive pupil
8. Spinal cord injury with hypotension
9. Severe ARDS ($\text{PaO}_2/\text{FIO}_2 < 100$)
10. Flail sternum or unilateral flail chest wall segment (2 places on ≥ 3 ribs)
11. Pulmonary contusion or lobar infiltrate visible on admission chest xray
12. Chronic lung disease with $\text{PCO}_2 > 60$ mmHg and $\text{HCO}_3^- > 32$ mmol/L
13. ICP >20 mmHg longer than 30 minutes despite hypertonic saline or mannitol therapy
14. Known heart failure (heart failure defined as EF < 20%)
15. CVP > 20 mm Hg with associated systolic blood pressure < 100 mmHg

15. Consenting process and plan

Study personnel will screen patients for inclusion and exclusion.

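### No upper limit on baseline PaO2/FiO2: some patients may have little room for a 20% rise, and with 19 per arm the unadjusted primary comparison is exposed to chance imbalance in them

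*Combined protocol and SAP*

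**What the plan says.** **Eligibility (section 14).** Patients are screened if they have traumatic head injury "requiring mechanical ventilation within 24 hours of admission". The other inclusion criteria are CT findings of injury and a negative pregnancy test. None concerns oxygenation. Severe ARDS (P/F below 100) and FiO2 above 0.65 are excluded, as are flail segments, pneumothorax needing a chest tube, and "Pulmonary contusion or lobar infiltrate visible on admission chest xray". No upper limit on P/F is set.

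**Background (section 5).** In a cited series of 21 brain-injured subjects without evidence of acute lung injury, the protocol reports: "On day 1, PaO₂/FIO₂ was > 400 (FIO₂= 0.46". A second cited series, of 21 head-injured patients, is described as hypoxaemic with increased shunt.

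**Endpoint and sample size (section 12).** Success is a change in the PaO2:FiO2 "ratio of 20 percent or greater between baseline and Day 3". The treatment-group proportion "is assumed to be 0.10 under the null hypothesis and 0.50 under the alternative hypothesis". For the comparator: "The proportion in group two (the control group) is 0.10". Groups of 19 and 19 are said to "achieve 82% power to detect a difference between the group proportions of 0.40". The test is a two-sided pooled z-test, with no adjustment for baseline. Section 12 also plans baseline comparisons by t-test or chi-square.

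**Allocation (section 6, step 6).** Randomisation follows the initial measurements. No stratification is described.

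**The concern.** P/F has a physical ceiling set by the inspired oxygen. A patient who starts close to it cannot show a large relative rise however well nitric oxide works, and is likely to count as a failure in either arm. The entry criteria remove the sickest lungs and leave the healthy end open. Being ventilated is not a proxy for poor oxygenation here: section 3 gives airway and CO2 control as reasons for ventilation, and section 5 notes that FiO2 may be raised for reasons unrelated to lung dysfunction.

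Two things are at stake. With arms of 19, a few more such patients on one side can move the observed difference appreciably, and the planned test makes no allowance for that. Also, the 0.50 success rate that carries the sample size comes with no source and no expected baseline P/F distribution, so a reader cannot tell whether it already averages over patients with little room.

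**Working it through.** **1. The plan's own figure.** Inputs from section 12: 19 per arm, 0.50 v 0.10, two-sided pooled z-test, nominal 0.05. For every pair of success counts (x, y), compute z = (x/19 − y/19) / √[p(1 − p)(2/19)], with p = (x + y)/38. Sum the binomial probabilities of the pairs with |z| ≥ 1.96.
- Power at 0.50 v 0.10: 0.8154.
- Significance level at 0.10 v 0.10: 0.0361.

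Both match the plan.

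**2. Where room runs out.** The documents give no ceiling, so the following are assumptions: sea level (760 − 47 = 713 mmHg), PaCO2 40 mmHg, respiratory quotient 0.8, and unchanged FiO2. The simplified alveolar gas equation gives maximum PaO2 = 713 × FiO2 − 40/0.8, so maximum P/F = 713 − 50/FiO2. A 20% rise is impossible from a baseline above that maximum divided by 1.2.

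| FiO2 | Maximum P/F | Highest baseline allowing +20% |
|---|---|---|
| 0.40 | 588 | 490 |
| 0.46 | 604 | 504 |
| 0.65 | 636 | 530 |

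The full alveolar equation gives slightly higher cut-offs: 498, 512 and 538. From a baseline of 400 the target is 1.2 × 400 = 480, below the ceiling of 604 at FiO2 0.46. A baseline of 400 therefore leaves limited room, but some.

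**3. Sensitivity of power.** The share f of patients without room is not in the documents; 10 to 40% is an assumed range. In scenario A they fail in both arms and the others succeed at 0.50 and 0.10, so the rates are 0.50(1 − f) and 0.10(1 − f). In scenario B they succeed at 0.10 in either arm, so the treated rate is 0.50(1 − f) + 0.10f and the control rate is 0.10. Exact power with 19 per arm:

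| f | A: rates | A: power | B: treated rate | B: power |
|---|---|---|---|---|
| 10% | 0.45 v 0.09 | 75% | 0.46 | 74% |
| 20% | 0.40 v 0.08 | 67% | 0.42 | 64% |
| 30% | 0.35 v 0.07 | 59% | 0.38 | 54% |
| 40% | 0.30 v 0.06 | 51% | 0.34 | 44% |

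If 0.50 is instead the average over all treated patients, power stays at 82%. Under scenario A, patients with room would then need a success rate of 0.50/(1 − f): 56, 63, 71 or 83%.

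**4. Chance imbalance.** Assume 8 of the 38 have no room. Under simple 19:19 allocation, the number x of them in one arm has probability C(8, x) C(30, 19 − x) / C(38, 19). The probability that x ≤ 2 or x ≥ 6, a split of 6-2 or worse, is 0.116 + 0.116 = 0.23.

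Expected observed differences, with 0.50 and 0.10 among patients with room and zero among the rest:
- 4 treated, 4 control: 15 × 0.50/19 − 15 × 0.10/19 = 0.395 − 0.079 = 0.316.
- 6 treated, 2 control: 13 × 0.50/19 − 17 × 0.10/19 = 0.342 − 0.089 = 0.253.
- 2 treated, 6 control: 17 × 0.50/19 − 13 × 0.10/19 = 0.447 − 0.068 = 0.379.

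The same treatment effect thus appears about 0.06 smaller or larger purely from where these eight patients fall.

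**5. Effect of stratifying.** In simulations with assumed shares of patients without room, stratified allocation with a stratified test gained roughly 0 to 6 points of power, with no cost in type I error. The higher gains suppose that the strata separate patients with and without room well; a cut at 400 would do so less cleanly.

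**The case against.** Several points on the other side stand.

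- **A reader might infer that the 82% is overstated.** The documents do not support that. Section 12 gives 0.50 as the proportion for the treatment group, and an overall 50% can already include patients who cannot respond. The 82% holds whenever the overall rates are 0.50 and 0.10, whatever the mix, so it would also be wrong to say that it requires every patient to have room.
- **A reader might infer that the criteria select near-normal lungs.** They permit them, but P/F from 100 to 300 remains eligible without visible contusion or lobar infiltrate, and aspiration is not an exclusion. The exclusions fit the stated rationale of altered perfusion rather than parenchymal disease.
- **The series with P/F above 400 does not show that anyone lacks room.** It mixed intracranial haemorrhage with head injury and had no evidence of acute lung injury, which this trial does not require. The figure lies below the 490 to 530 cut-offs, and the other cited series was hypoxaemic.
- **The cut-offs are not absolute.** They fix FiO2 and PaCO2, which may differ by Day 3. A baseline of 500 at FiO2 0.40 needs 600, and the ceiling at FiO2 0.65 is 636.
- **The endpoint says change, not rise.** Reading it as a rise is an inference, though the hypothesis of improved oxygenation in section 4 supports it.
- **Randomisation keeps the unadjusted test valid on average.** The distortion concerns the allocation actually obtained, and precision. Stratifying does not create room where there is none.

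The planned baseline comparisons do not answer the imbalance point: they may reveal an imbalance but neither prevent it nor correct for it.

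**Conclusion.** The point holds as a design weakness that is cheap to repair, not as an error in the power calculation. Eligibility sets no upper P/F limit and requires no oxygenation deficit, so patients with little room for a 20% rise can enter. Neither the allocation nor the primary test protects the comparison of 19 v 19 from an uneven spread of them.

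The size depends on an unknown. If 8 of 38 had no room, a 6-2 or worse split would occur about 23% of the time and shift the expected difference by about 0.06. The 82% is correct for its inputs; what is missing is a source for 0.50. The 75, 67, 59 and 51% figures are a sensitivity range that rests on two assumptions absent from the documents: that 0.50 applies only to patients with room, and that 10 to 40% have none. They are not an estimate of this trial's power.

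Nor do the documents establish a need for an upper P/F limit for randomisation. Studying ventilated head-injured patients at large is a legitimate choice, and a limit would trade accrual and generality for sensitivity.

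**What to change.** **Section 6, step 6.** Stratify the randomisation by baseline P/F, with a prespecified cut such as 400. Section 8 already provides for a baseline arterial blood gas, and the initial measurements precede randomisation. Because section 8 keeps patients in the study when a sample cannot be obtained, say how a patient without a baseline gas is to be allocated.

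**Section 12, primary analysis.** Replace the unadjusted z-test with a test that uses the stratum, for example Cochran-Mantel-Haenszel. Without this, stratified allocation balances the arms but the analysis does not use the stratum. State that the 20% change means a rise, if that is intended.

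**Section 12, sample size.** State that 0.50 is the expected rate over all treated patients, give its source, and show the sensitivity figures from the working. The 82% itself needs no correction.

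**Cost.** A few lines of text, a slightly more complex allocation list, and the need for the baseline blood gas result before allocation. No new measurement and no change to who is eligible.
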